#### **Consenting Clients**

There is one pathway to identify clients for participation in the study. For full details on the recruitment process, please see the HIPAA Recruitment Checklist. There will be one Centerstone Research Institute research assistant (CRI RA) responsible for sites located in Tennessee and one CRI RA responsible for sites located in Indiana. Centerstone Research Institute has established a system for identifying clients eligible for the various ongoing research projects. Specifically, each CRI RA will run queries of the Electronic Health Record system database daily to identify potentially eligible clients seeking individual psychotherapy for depression with enrolled study clinicians based on the above listed inclusion/exclusion criteria (all eligibility information is collected during the intake and stored in the database). The average time from intake to the first psychotherapy session at Centerstone is 13 days, which will provide ample time for eligible clients to be enrolled in the study prior to the first therapy session. However, to ensure that the potential participant is contacted in a timely manner before their first psychotherapy session, the queries will be run daily. Upon identification of potential eligibility, the CRI RAs will contact the client via telephone within 24 hours to perform an eligibility 10-20 minute phone screen. The initial phone screen (RCR.3) is to confirm eligibility for participation, which is based on having a PHQ-9 score greater than 9 and a willingness to participate in the study. The CRI RA will verbally administer the PHQ-9 (in its entirety) to confirm project eligibility. If the client is determined to be eligible, the CRI RA will go over the informed consent statement (study procedure, risks/benefits, confidentiality, etc.) and ask the client if s/he is willing to give verbal consent to participation in the study at that time or if s/he would like to first receive and review the informed consent statement and the authorization for the release of protected health information. The CRI will stress that participation is voluntary and that the client may withdraw consent at any time. Following the phone call, consented participants and those interested in consenting upon review of the informed consent statement will be mailed a Welcome Packet, which will contain the informed consent for the client's records.

Three days after the Welcome Packet is sent out, CRI RAs will then follow up with clients by telephone so that the client may have the opportunity to ask questions about the study. At this time, the CRI RAs may also offer to visit clients in person at their local Centerstone site or in their home (only if the RA is comfortable with this option) to discuss remaining questions about the research project further. Finally, although clinicians are not formally a part of the recruitment process, we have created an information sheet for clinicians in case his or her client has questions about the study the

clinician will be able to provide some background (RCR.8) and a client study brochure (Appendix F.2) that s/he can offer the client.

### **Consenting Administrators**

Administrators will first be sent a recruitment email with overall study information and their role in their study (RCR.5). Administrators will be consented via two pathways: 1) in person, implicit consent during the initial site visit staff meeting and 2) email recruitment with implicit consent. The implicit consent procedure is described here: 1) During a staff meeting at each site, a member of the research team will provide staff members with a welcome packet and verbally give information about the study. Food will be provided to each site administrator in attendance. The welcome packet will include a two administrator informed consent forms and the project coordinator's contact information. The research member will indicate that participation in the study is voluntary and will in no way affect their status as administrators at Centerstone. Administrators will have the opportunity to fill out the battery of measures thus giving their implicit consent to participation in person at this initial site visit or if the administrator would like to take additional time to review before filling out the battery and therefore consenting, s/he will be given a pre-paid, return-addressed envelope to mail the completed battery of measures when s/he is ready OR at the start of the next staff meeting a member of the research team will attend the first few minutes to answer questions and collect surveys. The email recruitment/ consent is detailed here: For those administrators who could not attend this staff meeting, a recruitment email (RCR.5) will be sent out to these administrators by a member of the research team with an e-version of the welcome packet for site administrators should they prefer to complete the battery of measures through an electronic survey option. Administrators may give their implicit consent to participation by filling out the baseline battery. These administrators will be contacted by CRI RAs directly to see if they have any questions or concerns about participating.

### **Consenting Office Professionals**

Office professionals will be recruited and consented via two avenues: 1) in person, implicit consent during the initial site visit and 2) email recruitment with implicit consent. The in person, implicit consent is described here: During a staff meeting at each site, a member of the research team will provide staff members with a welcome packet and verbally give information about the study. Food will be provided to each site office professional in attendance. The site administrator will send out an email (RCR.6) with information about this site visit to the office professionals. The welcome packet will include a two office professionals' informed consent forms, study recruitment letter (RCR.7), and the project coordinator's contact information. The research member will indicate that participation in the study is voluntary and will in no way affect their status as office professional at Centerstone. Office professional will have the opportunity to fill out the abbreviated battery of measures in person at this initial site visit or if the office professional would like to take additional time to review before filling out the abbreviated battery and therefore consenting, s/he will be given a pre-paid, return-addressed envelope to mail the abbreviated battery of measures when s/he is ready OR at the start of the next staff meeting a member of the research team will attend the first few minutes to answer questions and the abbreviated battery. For those office professionals who could not attend this staff meeting, 2) the site administrator for each site will place a welcome packet in those office professionals' mailboxes. State specific CRI RAs will then individually contact (via phone or email) these office professionals after a few days to see if s/he has any questions about the consent or participation process. The email recruitment/electronic implicit consent is described here: The other option for office professional recruitment and consent is via email recruitment for those office professionals who cannot attend the initial site visit with the research team. A recruitment email will (RCR.7) be sent out to these office professionals by a member of the research team with an e-version of the welcome packet should they prefer to complete the battery of measures through an electronic survey option. These office professionals will then have the option to implicitly consent by filling out the abbreviated baseline battery. These office professionals will be contacted by CRI RAs directly to see if they have any questions or concerns about participating.

### **Consenting Staff**

Staff will be recruited and consented via two avenues: 1) in person, implicit consent during the initial site visit and 2) email recruitment with implicit consent. The in person, implicit consent is described here: During a staff meeting at each site, a member of the research team will provide staff members with a welcome packet and verbally give information about the study. Food will be provided to each staff member in attendance. The site administrator will send out an email (RCR.9) with information about this site visit to the staff. The welcome packet will include two staff informed consent forms, study recruitment letter (RCR.7), and the project coordinator's contact information. The research member will indicate that participation in the study is voluntary and will in no way affect their status as a staff member at Centerstone. Staff will have the opportunity to fill out the abbreviated battery of measures in person at this initial site visit or if the staff member would like to take additional time to review before filling out the abbreviated battery and therefore consenting, s/he will be given a pre-paid, return-addressed envelope to mail the abbreviated battery of measures when s/he is ready OR at the start of the next staff meeting a member of the research team will attend the first few minutes to answer questions and the abbreviated battery. For those staff members who could not attend this staff meeting, 2) the site

administrator for each site will place a welcome packet in those staff members' mailboxes. State specific CRI RAs will then individually contact (via phone or email) these staff members after a few days to see if s/he has any questions about the consent or participation process. The email recruitment/electronic implicit consent is described here: The other option for staff recruitment and consent is via email recruitment for those staff who cannot attend the initial site visit with the research team. A recruitment email will contain the ICS be sent out to these staff members by a member of the research team with an e-version of the welcome packet should they prefer to complete the battery of measures through an electronic survey option. These staff members will then have the option to implicitly consent by filling out the abbreviated baseline battery. These staff members will be contacted by CRI RAs directly to see if they have any questions or concerns about participating.

2. **Who will be responsible for obtaining initial and ongoing consent? (check all that apply)**

- Principal Investigator
- Co-Investigator
- Other (specify): **Approved investigators, project coordinator, research assistants**

a. **Explain how these individuals will be adequately trained to conduct the consent interview and answer subject's questions (check all that apply):**

- Passed the required Collaborative Institutional Training Initiative (CITI) modules
- Attended the Research Coordinator Education Program (RCEP)
- Attended the Research Coordinator Certification Program (RCCP)
- Received study-specific training from study personnel
- Other (specify): HIPAA training, National Institutes of Health Human Subjects Training

b. **Indicate in what language(s) the consent interview will be conducted.**

- English
- Spanish
- Other (specify):

c. **If the consent interview will be conducted in a language other than English, state how the interview will be conducted (e.g. use of an interpreter):**

3. **Explain how subjects' privacy will be protected during the consent process.** This refers to how access to subjects will be controlled (e.g. time, place, etc. of consent procedures).

### **Clients**

A research assistant will call the potential client participant and ask if they are in a private setting and whether it would be convenient to speak about their interest in participating in the study. If it is not an optimal time for the client then the research assistant will schedule a more appropriate/convenient time in which to call the client back.

### **Administrators**

A CRI RA will give the administrator participants an opportunity to set up a separate time to offer more information and answer any questions the administrator would have at their convenience over the phone, via email, or in person at Centerstone.

### **Office Professionals**

A CRI RA will give the office professional participants an opportunity to set up a separate time to offer more information and answer any questions the office professional would have at their convenience over the phone, via email, or in person at Centerstone.

### **Staff**

A CRI RA will give the staff participants an opportunity to set up a separate time to offer more information and answer any questions the office professional would have at their convenience over the phone, via email, or in person at Centerstone.

1. **Indicate any factors that might result in the possibility of coercion or undue influence. (check all that apply)**

- the research will involve students of the investigator(s)
- the subjects will be recruited through institutions with which the PI has a close relationship
- Other (please specify): potential for clinicians to perceive coercion to participate in the study given that this proposal aligns with the agency's overall strategic goals.

**Describe steps taken to mitigate the possible coercion:** It is not possible to conceal clinician, administrator, or office professional study participation from supervisors. However, each supervisor will be instructed in human subjects research protections and made aware of the seriousness of research participant coercion in any form. Further, the supervisors and their managers will be instructed not to use participation in research as criteria for adjustment of wages or job position. The clinician, administrator, and office professional participant will be made aware of this risk and given the contact numbers of the compliance office at Indiana University to report any unfair treatment based on their participation, or lack of, in research. Moreover, even though we plan to randomize at the site level, not all clinicians at each site will need to participate in order for recruitment goals to be met. Therefore, clinicians will be explicitly informed that even though their site is enrolled and they may be eligible, there is no obligation to participate in the research.

**C. I am requesting a waiver of written documentation of informed consent (i.e. a consent process will occur, but no signature will be obtained from the subject).**

Written statement regarding the research has been attached. Statement will be provided to subjects upon their request. Please explain:

**Consenting Clients**

Clients will consent for participation in the study after completing the eligibility screening over the phone with a CRI RA. Once the client has been determined eligible the CRI RA will go over the informed consent statement (study procedure, risks/benefits, confidentiality, etc.) and authorization for the release of protected health information and ask the client if s/he is willing to give verbal consent to participation in the study at that time or if they would like to first receive and review the informed consent statement. The CRI will stress that participation is voluntary and that the client may withdraw consent at any time. At this time, the client may verbally consent to participation or call back after reviewing the informed consent statement. Following the phone call, consented participants and those interested in consenting upon review of the informed consent statement will be mailed a Welcome Packet, which will contain the informed consent for the clients record. After clients give their verbal consent to participation, they will be enrolled in the study and data collection can begin.

**Consenting Clinicians**

All clinicians who meet the inclusion criteria presented below and who provide services at any of the 12 Centerstone sites involved in the proposed research will be eligible for participation in the study. There are three pathways through which the clinicians will be recruited and one way they may consent to participate in the research. The research team will recruit clinicians for participation via email and site visits.

Recruitment Option 1: During a staff meeting at each site, a member of the research team will provide staff members with a welcome packet and verbally give information about the study. One hour of productivity credit coverage and food will be provided to each clinician in attendance. The site administrator will send out an email (RCR.1) with information about this site visit to the clinicians. The welcome packet will include two Clinician informed consent forms, a study recruitment letter (RCR.2), the baseline battery of questionnaires, and the project coordinator's contact information. The research member will indicate that participation in the study is voluntary and will in no way affect their status as clinicians at Centerstone. The recruitment letter as well as the research member(s) present at the meeting will inform clinicians that by filling out and returning the baseline battery of questionnaires to the researchers, s/he is agreeing to participate in the research project and all of its activities. However, if the clinician would like to take additional time to review the informed consent before implicitly consenting, s/he will be given a pre-paid, return-addressed envelope to mail the filled out baseline battery of questionnaires when s/he is ready OR at the start of the next staff meeting a member of the research team will attend the first few minutes to answer questions and collect the filled out battery of questionnaires.

Recruitment Option 2:

For those clinicians who could not attend this staff meeting, the site administrator for each site will place a welcome packet in the clinician mailboxes of those who could not attend. A research member will then individually contact (via phone or email) these clinicians after a few days to see if s/he has any questions about the consent or participation process.

Recruitment Option 3: The other option for clinician recruitment and consenting is via email recruitment for those clinicians who cannot attend the initial site visit with the research team. A recruitment email (RCR.2 [the bottom portion will be revised for email recruitment]) will be sent out to these clinicians by a member of the research team with an e-version of the welcome packet should they prefer to complete the battery of measures through an electronic survey option. This

recruitment email will have a link to the web-based survey of the baseline battery of questionnaires. Upon accessing the web-based survey, study participants will be presented with a web page containing the informed consent and will be informed that clicking the “proceed” button will be taken as implicit consent to the participate in the study and all its activities. This page will include the contact information of the research team, so participants may contact the researchers with any questions they may have. In addition, these clinicians will be contacted by a research member directly after being sent the recruitment email to see if they have any questions or concerns about participating.

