**Phase 2: Randomized Trial: Implementation & Sustainment.** Implementation will take place across 12 sites in months 8-38 using the dynamic waitlist control design (Brown et al., 2006; C15. Justification and Feasibility). Specifically, matched sites (based on size and urban/rural status) will be randomized to either early or later stage implementation in 4 cohorts (2-4 sites per cohort spaced 5 months apart), with half the sites randomized to the standardized and half to the tailored condition; see Figure 2 for a concise depiction of the implementation timing. The timing of this protocol is based on the published work of Miller et al. (2012) as well as the successful naturalistic MBC implementation at Group Health (personal communication, [name], February 11, 2014). Beginning at month 8, the earliest cohort (2 sites) will engage in the baseline mixed methods needs assessment (Assessment Time 1; AT1). Using purposeful sampling (Palinkas et al., 2013), a subset of clinicians (N=5-8 at each site) representing extreme variation (nominated by clinic directors based on their support for or against MBC implementation) will participate in a 1.5-hour focus group. This sampling approach is critical to gain a wide range of clinician views. Rapid ethnography will then be used to uncover site-specific insights that will guide the content of training and consultation in the tailored condition only (with the aid of mixed method expert [name]; C13b. Data Analysis Plan). During the needs assessment, all enrolled clinicians will complete the battery of baseline measures (see Table 5, Section II), from which the opinion leader (Childers, 1998) and self-nominated MBC champion will be identified and invited to join the implementation team. Across conditions, this team will convene triweekly during the 5-month active implementation period to ensure implementation strategy fidelity (Proctor et al., 2013) and review MBC fidelity. Following the needs assessment, clinicians will participate in a 4-hour MBC training workshop (see C9. Pilot Studies for content) and will begin triweekly consultation. To characterize the differences in implementation team meetings and consultation between conditions, sessions will be audiorecorded and contextual factors logged by graduate research specialist on the MBC Barriers Log (informed by the Framework for Dissemination; [name] et al., 2008; see Appendix for form template). Simultaneously a site team member will log meetings (using the same form) and data triangulated to calibrate site team members and prep for the exit of research personnel. Implementation/Process Evaluations ([name] et al., 2008; AT2) at the clinician level will occur 5 months after the needs assessment at which point the research personnel will be removed. The site implementation teams will be encouraged to continue meeting to promote MBC sustainment and the responsibility to log and address MBC barriers will transfer completely to the site team members. Outcome/Impact Evaluation ([name] et al., 2008; AT3) at the clinician and client level will occur 10 months after the Implementation/Process Evaluation. Focus groups will be held with the implementation team at AT3 to review their experience and the site's progress since the research personnel exited the team. All aforementioned steps will be repeated across the remaining three cohorts.

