### III. Clinician Measures: Implementation Outcomes

MBC Fidelity	1. If clients complete the PHQ-9, it will be captured in the EHR (0=No, 1=Yes). 2. The EHR will reveal whether clinicians reviewed scores (0=No, 1=Yes). 3. Clinicians will self-report if they discussed scores in session (0=No, 1=Yes). Clients will respond via text to indicate whether clinician initiated score discussion in session. Reasons for MBC fidelity deviation will be captured via clinician report on progress notes.	BL, AT2, AT3
--------------	---	--------------

*Note* BL(AT1) = Baseline(Assessment Time 1), AT2 = Assessment Time 2, AT3 = Assessment Time 3.

**Retention.** The total time required for clinician study participation is 15 months; however, the first two assessments are obtained within the first 5 months. The average length of employment for a clinician at Centerstone is 6 years with an average of 11.72% attrition last year. We anticipate stable clinician participation for the granting period. Fortunately, literature suggests that participatory approaches to organizational change in practice patterns result in lower clinician attrition (Minkler & Salvatore, 2012). Even so, we will recruit 1.25 times more clinicians ( $N=187$ ) to accommodate attrition and achieve the target ( $N=150$ ). Because of the dynamic waitlist design, we will revisit enrollment in Phase 2, 3 months prior to each site's planned implementation. Finally, the design can handle attrition given the within- and between-subjects analyses and multiple assessment points (3 ATs), as can the analyses (multilevel modeling with multiple imputation, described below).

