## **C. Number of Subjects.**

### **Clinicians**

Clinicians will be recruited from 12 Centerstone sites across two states (Indiana and Tennessee). Approximately 187 clinicians (average of 16 per site) will be recruited during the latter half of Phase 1 of the study (months 5 to 8) to achieve our target enrollment of 150 (accounting for clinician turnover) and allow for initial site randomization (to early or late and standardized or tailored implementation) to occur just prior to Phase 2 (months 8-38).

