#### **Phase 2 (Months 8 – 38)**

*5-Month Active Implementation.* Beginning at month eight, clinicians who provide individual psychotherapy to adults with depression (based on their self-reported typical and current caseload (i.e., clinicians will learn in the eligibility discussion that if they consent to participate in the study then they must have eligible clients to potentially enroll as well) and who conduct psychotherapy sessions in English will engage in the baseline mixed methods needs assessment. This assessment will consist of a battery of surveys and then, following the completion of these surveys a focus group will take place. Clinicians will be asked to complete the following baseline battery of self-reports (Appendix A): Demographic Questionnaire ([name] & Simons, 2011; Appendix A.1); Progress Monitoring Theory of Planned Behavior (Francis et al., 2004; Appendix A.2); Attitudes toward Standardized Assessment-Monitoring and Feedback (Jensen-Doss et al., *in press*; Appendix A.3); Monitoring and Feedback Attitudes Scale (Jensen-Doss et al., *in press*; Appendix A.4); Monitoring As Usual Measure (Lyon et al., 2015; A.5); Evidenced-Based Practices Attitudes Scale (Aarons, 2004; A.6); Survey of Organizational Functioning (Broome et al., 2007; A.7), Implementation Climate (Jacobs et al., 2014; A.8); Implementation Climate Scale (Earhart et al., 2014; A.9); Barriers and Facilitators to Implementing Survey (Salyers, Rollins, McGuire, & Gearhart, 2008; A.10); Sociometric Questionnaire (Valente et al., 2007; A.11); Opinion Leadership Scale (Childers, 1986) and self-nomination question (A.12); Implementation Leadership Scale (Aarons et al., 2014; A.13); and Perceptions of Adopting Measurement-Based Care (Moore & Benbasat, 1991; A.14). All questionnaires will be completed online using assessment software by emailing them a link or via hard copy (in-person). These questionnaires will take about 60 minutes to complete and clinicians who complete the baseline assessment will receive \$50 compensation. Using the data from these surveys, a subsample of clinicians at each site, selected using purposeful sampling for extreme variation (Palinkas et al., 2013), will be asked to participate in a 1.5 hour focus group (Appendix E.1). Clinicians who participate in the focus group(s) will receive \$25 compensation. Focus groups will be recorded and transcribed with data de-identified for the purposes of qualitative coding. Staff who do not provide individual psychotherapy to adults with depression in English (for example, this could be clinicians who primarily provide therapy to children, groups, diagnoses other than depression and/or conduct therapy in another language; or psychiatrists, nurses, nurse practitioners, case managers, other non-clinical staff) will engage in an abbreviated version of the battery of self-report measures which will include: (Appendix A): Demographic Questionnaire ([name] & Simons, 2011; Appendix A.1); Progress Monitoring Theory of Planned Behavior (Francis et al., 2004; Appendix A.2); Attitudes toward Standardized Assessment-Monitoring and Feedback (Jensen-Doss et al., *in press*; Appendix A.3); Monitoring and Feedback Attitudes Scale (Jensen-Doss et al., *in press*; Appendix A.4); Evidenced-Based Practices Attitudes Scale (Aarons, 2004; A.6); Sociometric Questionnaire (Valente et al., 2007; A.11); Opinion Leadership Scale (Childers, 1986). All questionnaires will be completed online using assessment software by emailing them a link or via hard copy (in-person). The questionnaires will take less than 30 minutes to complete and staff who complete the abbreviated baseline assessment will receive \$20 in compensation per assessment point. Note, from this point forward we will refer to this group of staff as the “general staff” to differentiate them from those completing the full baseline battery which we will refer to as simply “clinicians.”

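### The documents disagree on whether clinicians consent before site randomisation, and enrolment reopens after it in cohorts 2 to 4 with nothing stated to conceal the site's condition

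*Combined protocol and SAP*

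**What the plan says.** **Recruitment before randomisation.** Section V.C (Number of Subjects, Clinicians) says that about 187 clinicians "will be recruited during the latter half of Phase 1 of the study (months 5 to 8"), in order to "allow for initial site randomization (to early or late and standardized or tailored implementation) to occur just prior to Phase 2 (months 8-38"). C12a (Recruitment) puts the start of clinician enrolment and the site randomisation in the same months 5 to 8 without fixing their order. The phase summary in Section VII and its Phase 1 text for clinicians also place recruitment in Phase 1. C12a (Data Collection) labels the baseline needs assessment Phase 1.

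**Consent through the battery.** Section XII (Consenting Clinicians) describes three recruitment pathways but "one way they may consent to participate in the research". On paper, consent is the return of the baseline battery: "by filling out and returning the baseline battery of questionnaires to the researchers, s/he is agreeing to participate in the research project". In the email pathway it is a click into the web version: the "button will be taken as implicit consent to the participate in the study and all its activities".

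**Battery from month 8.** Section VII (Clinicians, Phase 2) schedules the baseline needs assessment, including the battery, from that point: "Beginning at month eight, clinicians who provide individual psychotherapy to adults with depression" take part in it. C11 (Phase 2) starts the first cohort at month 8, spaces the four cohorts 5 months apart, and adds: "All aforementioned steps will be repeated across the remaining three cohorts".

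**Enrolment reopened.** C12a (Retention): "we will revisit enrollment in Phase 2, 3 months prior to each" site's start.

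**Concealment.** No passage keeps a site's condition from its clinicians, administrators or recruiting staff until consent is complete. No passage says that they are told it beforehand either.

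**The concern.** Sites are randomised, but clinicians choose individually whether to take part; Section IX stresses that they have no obligation to do so. If that choice is made after the site's condition is set and could be known, the two arms can recruit different kinds of clinician. The arms ask for different things: PHQ-9 at every session in one, a schedule set by the site in the other. That gives a reason why willingness to join might differ.

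H1a, half of the co-primary aim, compares clinician behaviour between the arms. The safeguards in C13a do not reach this problem. Intention-to-treat and multiple imputation cover participants, not clinicians who never consented. The H1a models contain time, group, their interaction and patient status, but no clinician attitude or intention measure that could adjust for selection.

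**Working it through.** **1. Timeline.** Inputs: Phase 2 starts at month 8, four cohorts 5 months apart (C11, Phase 2); 5 months active plus 10 months sustainment per cohort (C11, Phase 1); enrolment revisited 3 months before each start (C12a, Retention).

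Check against the plan's own figure: the end of cohort 4 is 8 + 3×5 + 5 + 10 = 38, the stated end of Phase 2. The schedule is reproduced.

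Start of cohort k = 8 + 5(k − 1); re-enrolment = start − 3.

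| Cohort | Battery (month) | Months after a month-8 randomisation | Re-enrolment (month) | Months after a month-8 randomisation |
|---|---|---|---|---|
| 1 | 8 | 0 | 5 | −3 |
| 2 | 13 | 5 | 10 | 2 |
| 3 | 18 | 10 | 15 | 7 |
| 4 | 23 | 15 | 20 | 12 |

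No exact randomisation date is given. If it could fall anywhere in months 5 to 8, the cohort 4 battery comes 15 to 18 months later (23 − 8 to 23 − 5).

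**2. The two readings.**
- *Consent first:* recruitment in months 5 to 8, the Phase 1 label on the baseline assessment, the battery included in the recruitment packet (Section XII), and C11's statement that clinicians already enrolled complete the battery.
- *Consent after:* the battery is the act of consent, and it is scheduled from month 8, cohort by cohort.

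These cannot both hold for cohorts 2 to 4 unless the battery is given twice or much earlier than C11 and Section VII say. The re-enrolment step does not depend on which is right: months 10, 15 and 20 follow randomisation in both.

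**3. Scope of the re-enrolment step.** C12a (Retention) gives 11.72% clinician attrition last year. If that rate held (an assumption), the share leaving within m months is 1 − (1 − 0.1172)^(m/12): about 5% at 5 months, 10% at 10 and 14% at 15. The plan does not say how many places would be refilled.

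**4. Illustrative size of a selection effect.** Suppose intention is normal and the lowest fraction p declines in one arm only. Mean intention there rises by φ(z_p)/(1 − p); multiplying by the pilot correlation between intention and PHQ-9 use, r = .67 (C9), gives the shift in mean use.
- p = .10: .1755/.90 = .195; × .67 = 0.13 SD.
- p = .20: .2800/.80 = .350; × .67 = 0.23 SD.

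The 10% and 20% are assumptions. Set against the smallest detectable clinician effect, d = .46 (C13a, Power calculations), the shifts are 28% and 51% of it.

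**5. Precision of that r.** C9 gives p = .036 without the number of clinicians behind the correlation. With n = 10, t = .67 × √(8/(1 − .4489)) = 2.55 and p = .034, so n is about 10. By Fisher's transformation, .811 ± 1.96/√7 runs from .070 to 1.552, so r runs from about .07 to .91. The 10% shift is then 0.01 to 0.18 SD and the 20% shift 0.02 to 0.32 SD, or 3% to 70% of .46.

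**The case against.** The strongest reply is that several passages plainly intend enrolment before randomisation, and that nothing shows clinicians learning their condition before they consent. The recruitment letter and emails are not reproduced in the text available. Training, which introduces the arm's approach, follows the needs assessment. In tailored sites the schedule does not yet exist when the battery is returned, because the implementation team sets it within the first month and some team members are picked from the battery. C12a also reports that clinicians unsupportive of MBC agreed to take part in the pilot, and C9 reports full clinician participation in its needs assessment.

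Most of this stands as a limit on the claim. It rules out stating that clinicians enrol only after randomisation or that they know their condition. It does not remove the exposure. A clinician need not know the tailored schedule to know which approach the site was assigned, and in cohorts 2 to 4 other sites of the same organisation will already be active. The plan itself includes a contamination interview with administrators (Section VII). The pilot had no randomised conditions, so it cannot show that refusal would be equal between arms.

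The size is also open to challenge, fairly. The calculation assumes that refusal occurs in one arm only and follows intention perfectly. The pilot correlation pools two sites that differed in intention-related measures, in use and in technical failures. The d of .46 comes from a growth-model power calculation, whereas H1a is analysed with an encounter-level logistic mixed model, so the ratio is only a rough yardstick.

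**Conclusion.** The documents contradict themselves on whether clinician consent precedes site randomisation. Independently of that, they reopen enrolment after randomisation for cohorts 2 to 4 without stating that the condition is concealed. Differential self-selection could therefore bias H1a. The timeline arithmetic is firm, given a randomisation at or before month 8.

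A reader might infer that every clinician opts in or out knowing the arm. The documents do not support this: the Phase 1 recruitment passages point the other way, and disclosure before consent would be read into silence. A reader might also infer that reluctant clinicians would leave the standardized arm and bias the trial against H1a. That is plausible, but nothing in the documents establishes the direction.

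The 0.13 and 0.23 SD figures rest on assumed one-sided refusal and a small-sample correlation. They show that the effect need not be trivial; they do not estimate it. The point should be addressed because protection is nearly free and the planned analysis cannot repair the bias afterwards.

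**What to change.** 1. Withhold each site's condition (standardized or tailored) from site staff, clinicians and recruiting staff until clinician consent and the baseline battery have closed at that site. Release only the start date. This is workable: C10 puts the needs assessment before team formation, guideline and training, and both arms run it.
2. Reconcile C11 (Phase 2), C12a (Recruitment and Data Collection), Section V.C and Section VII on when consent and the battery occur. Moving the recruitment passages to match the month-8 schedule would by itself entrench enrolment after randomisation.
3. Record each clinician's consent date relative to randomisation and to disclosure. Report the numbers approached, consenting and declining by condition.
4. Keep clinicians who consented after disclosure in the primary H1a set, since the top-up exists to cover attrition, and run H1a without them as a sensitivity analysis.

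Parts of C13a are in the past tense and give an observed rate of missing 12-week interviews, so enrolment may have closed. In that case item 1 is no longer possible, but the reporting and sensitivity analysis still apply wherever dates were kept.

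Cost: a little record-keeping and one extra analysis.
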